Protocol

Disseminating Public Health Evidence to Support Prevention and Control of Diabetes Among Local Health Departments

NCT03211832

Updated October 11, 2021

A Stepped Wedge Cluster Randomized Controlled Trial

We will conduct a stepped wedge cluster randomized controlled trial of 12 local health departments (LHDs) in Missouri to evaluate the effectiveness of active D&I approaches on perceived individual and organizational capacity for evidence-based decision making in prevention of diabetes and other chronic diseases.

LHDs will be randomly assigned to three groups that crossover to receive the intervention with measurements at 8-month intervals. No LHDs receive the intervention at baseline. All participating 12 LHDs will receive the intervention, however, for varying durations; group 1 crosses over from control, i.e., usual practice to receive the intervention activities first and for a total of 24 months, group 2 crosses over second and receives the intervention for 16 months, and group 3 crosses over last and receives the intervention activities for 8 months. The intervention activities include a flexible "menu" of D&I approaches that account for local contextual and organizational factors. Dissemination strategies are designed to build workforce and organizational capacity, and may include training in evidence-based public health, technical assistance through a knowledge broker, providing targeted messages/emails with a short summary of the research and actions that might be taken based on the evidence, and organizational changes to assist agency leadership in prioritizing, incentivizing and incorporating the use of EBPPs. LHD practitioners can choose intervention activities from this "menu". This "menu" approach avoids the pitfalls of a "one-size-fits-all" process that is unlikely to be effective across the 12 participating LHDs. Therefore, this study will not attempt to evaluate a single D&I intervention activity but will pursue active, multi-modal approaches, since these are supported in the literature.

Local Health Department Enrollment

Of the twelve LHDs selected, at least 3 will come from LHDs in counties with high diabetes disparity (highest tertile). Once all LHDs are recruited, each will be randomly assigned to one of three groups with four LHDs to a group. At least one LHD from high diabetes disparity will be randomly assigned to each group. Each group of LHDs will cross over to the intervention at 8-month intervals. To account for varying sample sizes for small versus large LHDs, we will limit our sample to LHDs with at least 5 employees working in or supporting chronic disease control and on the upper end no more than 22 individuals in larger LHDs. We will also include an additional 5-10 individuals (an average of 8) from partner agencies in each local community that include non-governmental organizations (e.g., local hospital, American Diabetes Association) and governmental organizations outside of the health sector (e.g., universities, parks/recreation, schools).

LHD selection will be based in part on the total number of full-time equivalent (FTE) employees (number of FTEs increases with size of population served by LHD), number of employees working in or supporting diabetes or chronic disease control, and diabetes burden, specifically mortality rate for diabetes as underlying cause (a measure of health disparity). Of the 12 LHDs selected and recruited, at least three will come from LHDs in counties from the highest tertile of mortality rate for diabetes as underlying cause. To be eligible, LHDs are required to have ≥ 5 employees working in or supporting diabetes or related areas in chronic disease control, which includes program areas of diabetes prevention and management, obesity prevention, physical activity, nutrition, cardiovascular health, school health, and cancer screenings. In addition, each LHD must have a designee to work with the study team on aspects of the intervention. LHDs will be assigned to one of three groups (four LHDs to each group) using simple random concealed allocation performed by the statistician.

LHDs with a total number of FTEs ≥ 35 or serving a population of $\geq 200,000$ are anticipated to have an adequate number of employees working in diabetes and chronic disease control. The project manager (RP) contacted directors at LHDs with 25-34 FTEs and serve a population of $<200,000$ (8 LHDs) to determine if their LHD has ≥ 5 employees working in diabetes prevention and management, obesity prevention, physical activity, nutrition, cardiovascular health, or cancer screenings; 5 of the 8 LHDs met this criterion. Of eligible LHDs (17 of 115 LHDs), those with the greatest diabetes burden (i.e., in the highest tertile for mortality rate for diabetes as underlying cause) followed by LHDs with the largest total number of FTEs employees will be contacted and recruited. Random assignment of the first 12 selected LHDs to groups will be performed. The principal investigator will invite local health directors from each selected LHD to have their employees working in diabetes and chronic disease control participate in the study. If any LHD declines, the next LHD according to total number of FTE employees will be selected. All employees working in or supporting diabetes and chronic disease control in participating LHDs will be invited into the study (complete listing), and a purposive sample of individuals from partner agencies (other governmental and non-governmental) in each LHD local community will also be invited. LHDs' key partners will be recruited into the study with the help of the chronic disease managers and other practitioners. We anticipate a range of 5 to 22 participants from the LHDs, coupled with staff from partner agencies for an average of 22 per jurisdiction.

Participants will be diabetes and chronic disease control directors, program managers and staff, and leadership from recruited LHDs in Missouri as well as staff from their key partner agencies. It is anticipated the participants will be from diverse backgrounds including health educators, epidemiologists, community health nurses, and persons with business backgrounds.

Each LHD will have a designee (most likely the lead chronic disease staff person) who will provide the project coordinator a contact list of staff and practitioners working in and supporting chronic disease control, agency leadership, and staff at key partner agencies. The project/study coordinator will send an email to the list of contacts at the measurement time points (baseline, and three 8-month intervals) inviting them to participate in the dissemination survey. For the network analysis instrument, the invitation will occur at baseline and the last measurement time point.

Table. Stepped wedge group randomized study design.

Shaded cells represent intervention periods (24 months, 16 months, or 8 months).

| | Months | | | |
|-----------------------------|--------|------------------|------------------|-----------------|
| | 1-2 | 3-10 | 11-18 | 19-26 |
| Group 1 (4 LHDs) | | 24 months | | |
| Group 2 (4 LHDs) | | | 16 months | |
| Group 3 (4 LHDs) | | | | 8 months |

For the web-based/online surveys (dissemination survey and network analysis instrument), the first page will be a cover letter containing all elements of consent. The cover letter will include a portion where individuals will be able to choose the statement that best describes how the individual would like to proceed ("Yes, I would like to take the survey," or "No, I prefer not to take the survey."). If a person clicks "Yes, I would like to take the survey," this will indicate her/his consent and s/he will be directed to the start of the survey. If a person clicks "No, I prefer not to take the survey," this will indicate s/he does not consent and s/he will be directed to the end of the survey and no follow up invite/reminders will occur. Project staff will conduct follow up through email and telephone contact. In all contact with potential participants, project staff will emphasize that participation is voluntary. Specifically, health department personnel will be informed that if they choose to take part, they can change their mind and leave the survey. Further, they will be informed that any refusal to participate or withdrawal will not involve a penalty or loss of benefits to which they are otherwise entitled.

Intervention: Individual and Organizational Capacity Building Activities

The capacity building (intervention) activities seek to build workforce and organizational capacity, and to effectively package and provide information so that it is timely, relevant, and useful for various local-level practitioners. There will be a menu of capacity building (intervention) activities in which each LHD can choose depending on what the LHDs deems important, relevant and feasible. The intervention period for groups begins with workshops as described below. A full set of examples of capacity building activities is shown in an attached table (Intervention Activities). A narrative summary of potential activities are listed below.

1. Targeted dissemination workshops – promoting the use of EBPPs will be modeled after successful workshops that have been conducted to promote evidence-based decision making (Brownson et al., 2009, Gibbert et al., 2013). The workshops will seek to enhance participants' abilities to: understand the role of EBPPs in addressing the diabetes burden; identify diabetes control strategies recommended by evidence-based reviews (e.g., the Community Guide); adapt EBPPs to address health disparities; address organizational barriers to EBPPs; and take action steps to move toward implementation and evaluation of EBPPs. All workshops incorporate principles of science-based training, including: an informal setting, team training, experiential learning, and small group activities applicable to real world experiences. A sample workshop agenda with a brief description of the modules is attached to this IRB form (EBPH Workshop Agenda).
2. Knowledge brokers – provide a link between research and practitioners by developing a mutual understanding of goals and cultures, collaborating with end users to identify problems for which solutions are required, and enhancing access and use of research evidence in practice and policy. This dissemination strategy has been used more in Canada than in the US. Although the public health literature is sparse with evaluations of knowledge broker impact, there is considerable evidence of effectiveness in other fields, particularly from business and agricultural sectors (Hargadon 2005, Verona et al., 2006, Zook 2004). The knowledge broker activities include: assistance with needs assessments and strategic planning that incorporate EBPPs; consultation on overcoming barriers to EBPPs; help with grant writing that incorporates information from evidence-based sources; and participation in the dissemination workshops described below. Interaction with the brokers will be one-on-one (broker to individuals and teams within the LHD) and it includes face-to-face contact, and remote telephone, email, and video communication.

3. Organizational changes – during the intervention period for each LHD, the research team will work with the LHDs to identify and implement a range of strategies to foster organizational change consistent with Institutional Theory that is part of the project's conceptual framework. Examples of strategies that will be employed will seek to: identify ways agency leadership can prioritize use of EBPPs, develop incentives for use of EBPPs, and incorporate EBPPs as a core component of agency practices (e.g., performance reviews, contracts with local partners).

Data Collection

To evaluate the impact of these intervention activities, we will:

- 1) ask staff/practitioners working in/supporting chronic disease control at each LHD, and their partner organizations to complete the online dissemination survey at four time points (baseline and three 8-month intervals);
- 2) ask for LHD records - program plans and progress reports that LHDs submits to funders, such as the Missouri Department of Health and Senior Services at two time points (baseline and the last data time point);
- 3) ask for information on the external partnerships of each LHD (baseline and the last data time point), and then ask LHD leadership - manager level and above to complete the online network analysis survey at two time points (baseline and the last data time point). The surveys will be designed for minimal time burden (about 20 minutes).

Power Analysis

This study uses a stepped wedge cluster randomized design. Based on our preliminary studies and values of ICC in the literature, we estimated a range of effect sizes and ICCs. ICC estimates are the most difficult to obtain. We calculated a median ICC from similar studies and developed a range based on a 50% decrease and increase around the median (range 0.009 to 0.027). The sample size requirement is based on testing hypotheses with a power of >90% and the overall Type I error of 5% given 12 clusters (LHDs). The null hypotheses suggest there would be no change in the scores from baseline of three outcomes—awareness, adoption, and maintenance—in all three groups of LHDs (no change). Drawing from our previous work, we hypothesize that the scores will be 17%, 20%, 14% higher for awareness, adoption, and maintenance from baseline to end of study, respectively. Following Baio et. al., and using the most conservative estimates of effect sizes and ICCs, we estimate a need for 12 LHDs, 3 steps or groups (of LHDs), and 10 subjects in each LHD (total = 120) to ensure 5 at the last measure/end of study (total = 60).

Analysis Plan

Descriptive statistics for participant and LHD characteristics and main outcomes will be conducted by trial mode. We will calculate gap in each skill for EBDM by subtracting availability from importance Likert rating (possible range of -10 to +10). An overall skill gap will be created by taking the average across all 10 skill items. We summed all 8 possible EBIs to calculate an “EBI score” which had a possible range of 0-8. For organizational culture items, we grouped and averaged Likert items within six main focus areas based on previous work: awareness of culture supportive of EBDM, capacity and expectations for EBDM, resource availability, evaluation capacity, EBDM climate cultivation, and partnerships to support EBDM (20). A confirmatory

factor analysis using data from all four time points according to standard procedures demonstrated adequate fit and strict measurement invariance of the factor structure used for the national survey in an earlier study phase. We used linear mixed-effect regression models for each outcome with LHD and Participant entered as random intercepts, trial mode (control or intervention) as fixed effect, and time as a categorical fixed effect. Public health degree, years worked in the public health field, job position category and accreditation status were entered as fixed effects. Kenward-Rogers approximations will be used to determine significance of fixed effects, a common approach in fitting restricted maximum likelihood models in order to produce acceptable Type 1 error. Where models violated assumptions of homoscedasticity, robust models will be approximated. Survey data will be cleaned initially in SPSS and then managed and analyzed in R.

Table. Summary of individual and organizational capacity building (intervention) activities

| Domain | Activity | Description |
|----------------------------------|--|--|
| Accreditation | Accreditation preparations | Local health assessment and plan, formalized decision making, documentation of evidence, documentation reviews, site visit, approval |
| Access to scientific information | Targeted messages | Participants will receive an email indicating that a systematic review related to diabetes or chronic disease control is available |
| Workforce development | Evidence-based decision making (EBDM) training (dissemination workshops) | In-state, in-person multi-day training in EBDM skills, 9 modules, as initial study intervention (this is the kick-off activity for the entire study) |
| | Supplemental brief EBDM skill trainings | Provided by study team or state chronic disease unit, in-person or webinar, as part of this study, with 3 states emphasizing evaluation skills |
| | Non-study national trainings | Hosted in-person EBDM-related skill trainings by national organizations and/or encouraged out-of-state training beyond those required by funders |
| | Quality improvement | Quality improvement or performance management trainings, guidance |
| | New employee EBDM orientation | Via archived webinars or course materials, facilitated discussions, meetings |
| Leadership, management supports | Chronic disease leadership teams expect EBDM | Leaders and supervisors continually ask 'what is the evidence', communicate EBDM expectations to staff, champion EBDM, encourage use of data for decision making, encourage skill building |
| | Use of data for decision making | Use data to prioritize programs, develop work plans, and monitor progress; share performance measures, data on intranet or centralized data systems |
| | Centralized data systems | Dashboard development to prioritize, measure, and track objectives and link to evidence base; share performance measures and data |
| | Meetings incorporate EBDM | Work unit and cross-section meetings address EBDM, present evidence, plans; (in leadership and in training) |

| | | |
|--------------------------------|--|--|
| | Performance reviews and EBDM | Work unit employee evaluations include objectives on EBDM learning and application |
| | Hiring practices address EBDM | Job descriptions, interview questions address EBDM; hire people with public health competencies; hire specialty staff including evaluators and epidemiologists |
| | Participatory decision making | Staff and partner input obtained, sharing of information for decision making |
| | Common language for EBDM | Creating and using common EBDM language across program areas |
| | Administrative reorganization for coordination | Organizational restructuring at the unit or section levels to increase coordination across programs and conduct joint projects across programs |
| Organizational changes | EBDM engrained | EBDM an embedded inseparable aspect of day-to-day work; strong expectation from leadership; high priority |
| | Learning orientation | Culture supports professional development and ongoing learning, providing links to webinars, bringing in guest speakers |
| Relationships and partnerships | Partnerships with in-state universities | Ongoing partnering for evaluation, trainings, internship placement |
| | Partner technical assistance and training | Phone and in-person guidance for partners' evidence-based work plans, evaluation, logic models; Provide EBDM trainings to partners |
| | Relationship building | Active steps to build or maintain positive partner relationships with open communication, trust, mutual respect, ensuring partner engagement and coalition development |
| Financial practices | Performance-based contracting | Funded partners required to implement evidence-based approaches as prescribed or selected from a menu, with performance objectives, work plans, and evaluation; holding contracted partners accountable for evidence-based interventions |
| | Proposals approved internally for EBDM prior to submission to funder | Local health department pre-approval process for grant applications to funders with requirements to show objectives, evidence basis, performance measures, evaluation plan |

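### The trial is powered on three outcomes at an overall 5% error, but the analysis tests other scores, names no primary, and has no multiplicity rule

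*Combined protocol and SAP*

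**What the plan says.** The opening section gives the target as "perceived individual and organizational capacity for evidence-based decision making in prevention of diabetes" and other chronic diseases. That names two broad domains and no score.

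The Power Analysis sizes the trial by "testing hypotheses with a power of >90% and the overall Type I error of 5" per cent. It continues: "The null hypotheses suggest there would be no change in the scores from baseline of three outcomes", and lists awareness, adoption and maintenance. None is ranked above the others. It does not say whether the tests are two-sided or what level each test uses.

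The Analysis Plan refers to main outcomes without listing them: "Descriptive statistics for participant and LHD characteristics and main outcomes will be conducted by trial mode". It then defines its scores:

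- Skill gap: "An overall skill gap will be created by taking the average across all 10 skill items". A gap is also calculated for each of the ten skills.
- Evidence-based interventions (EBIs): "We summed all 8 possible EBIs to calculate an" EBI score running from 0 to 8.
- Organizational culture: "we grouped and averaged Likert items within six main focus areas based on previous work".

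On testing, it says: "We used linear mixed-effect regression models for each outcome with LHD and Participant entered as random intercepts". Trial mode (control or intervention) is a fixed effect. Its only device for controlling Type I error is the Kenward-Rogers approximation.

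**The concern.** The three powered outcomes and the analysed scores are two different lists, and nothing joins them. One culture area carries awareness in its label, and a count of EBIs could stand for adoption, but the plan states neither link. No score evidently stands for maintenance. A reader therefore cannot tell which model tests which powered hypothesis.

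There is also no primary outcome, hierarchy, requirement that all outcomes succeed, or adjustment across models. Kenward-Rogers improves the error rate of a test within one small-cluster mixed model. It does nothing about the number of models. What is at stake is the meaning of a significant trial-mode effect on one score among several: the plan does not say whether that confirms a powered hypothesis, or what false-positive rate stands behind it.

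**Working it through.** **Inputs from the documents.** Overall Type I error 5%, power above 90%, and three powered outcomes (Power Analysis). Summary scores (Analysis Plan): 1 skill gap + 1 EBI score + 6 culture averages = 8. This count is derived; the plan gives no total.

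**Assumptions.** Each score is tested at two-sided 5%. All null hypotheses are true. Test statistics are normal with a common pairwise correlation ρ, shown from 0 to 0.9. The documents give no correlations.

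**Step 1: the plan's own figures.** One test at 5% gives 1 − 0.95 = 5%. Several tests at 5% each return 5% only if they are perfectly correlated. The sample size of 120 cannot be reproduced, because the effects are percentage increases (17%, 20%, 14%) with no baseline score or standard deviation.

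**Step 2: family-wise error without adjustment.** For independent tests it is 1 − 0.95^k:

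- k = 3: 1 − 0.95³ = 14.3%
- k = 8: 1 − 0.95⁸ = 33.7%

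For ρ > 0 it is 1 − P(all |Z| < 1.960), by numerical integration over a shared normal factor:

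| Scores tested | ρ = 0 | ρ = 0.5 | ρ = 0.7 | ρ = 0.9 |
|---|---|---|---|---|
| 3 | 14.3% | 12.5% | 10.9% | 8.4% |
| 8 | 33.7% | 25.0% | 19.1% | 11.9% |

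Scores from one survey are likely to be positively correlated, so the right-hand columns are more plausible than ρ = 0.

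**Step 3: per-test level needed for 5% overall.** Solving the same expression for a common level gives 1.70% (ρ = 0) to 2.89% (ρ = 0.9) for three scores, and 0.64% to 1.88% for eight. The plan states no such level.

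**Step 4: cost of Holm.** Take a test with exactly 90% power at two-sided 5%. Its expected Z is 1.960 + 1.282 = 3.242. At the strictest Holm step:

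- Three scores, level 0.05/3, critical value 2.394: Φ(3.242 − 2.394) = 80.2%
- Eight scores, level 0.05/8, critical value 2.734: Φ(3.242 − 2.734) = 69.4%

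Later Holm steps use less strict levels and lose less.

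**The case against.** The strongest objection concerns the word overall. It appears once, in a sample-size sentence beside power and cluster count, where one normally states the alpha used. It may mean no more than that. This stands. A reader might infer that the plan promises family-wise control and then breaks the promise, but the documents do not settle that reading. The missing primary, mapping and multiplicity rule do not depend on it.

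The error rates are also generic. The per-test level, sidedness and correlations are assumed, and the family of eight is inferred from the phrase about each outcome. Testing the ten single-skill gaps as well would enlarge the family. This stands too, so the percentages are illustrations and not estimates for this trial.

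The mapping gap is not total, since awareness and adoption have plausible counterparts. That narrows the gap without closing it, because the plan states neither link.

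The Holm cost may be overstated. The plan claims more than 90% power using its most conservative inputs and 10 subjects per LHD, whereas the enrollment section anticipates an average of 22 per jurisdiction. A larger sample would soften the loss, provided that the analysed scores show the effects assumed for the powered outcomes.

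Finally, a reader might infer that favourable scores will be picked out after the fact. Nothing in the documents shows this. The Analysis Plan does report a factor analysis on all four time points and describes some steps in the past tense. That bears on how a later choice should be labelled and is not evidence of selective reporting.

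**Conclusion.** The concern holds in a limited form. The plan names no primary outcome, links no analysed score explicitly to awareness, adoption or maintenance, and has no rule across models. These are omissions in the text and need no assumption.

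If the 5% is meant to cover all hypotheses and each score is tested at two-sided 5%, it is not delivered. The illustrative family-wise error is about 8–14% for three scores and 12–34% for eight, and even at correlation 0.9 eight scores more than double the stated rate. If the 5% is only the sample-size alpha, no commitment is broken, but the 5% and the power above 90% still attach to outcomes that the Analysis Plan does not identify. On either reading the text should be corrected.

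**What to change.** 1. State which analysed score represents each powered outcome. If maintenance has none, say so.
2. Apply Holm at an overall two-sided 5% to the trial-mode tests of the mapped scores, and label the other scores secondary. If no mapping can be made, apply Holm to all eight summary scores.
3. Report all eight estimates with confidence intervals and unadjusted p-values, with adjusted p-values for every score in the Holm family. Treat the ten single-skill gaps as descriptive.
4. Label as post hoc any mapping or choice of family made after the four-time-point data were used.
5. If no adjustment is made, replace the overall 5% statement with *5% per test, unadjusted* and present the results as exploratory.

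This takes one mapping statement and one rule applied to p-values already planned, with no new participants, data or models. The price is power: a test with exactly 90% power at 5% falls to 80% (three scores) or 69% (eight) at the strictest Holm step. If the assumed effects hold, that is a worst case, because the plan claims more than 90%. A mapping made now carries a post hoc label, and step 5 gives up a confirmatory claim.

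### The skill outcome is modelled only as importance minus availability, so by itself it cannot show whether available skills changed

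*Combined protocol and SAP*

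**What the plan says.** In the Analysis Plan, the score for each skill in evidence-based decision making (EBDM) is obtained by "subtracting availability from importance Likert rating", with a "possible range of -10 to +10". The item scores are then combined: "An overall skill gap will be created by taking the average across all 10 skill items". The modelling text reads "We used linear mixed-effect regression models for each outcome with LHD and Participant entered as random intercepts", with trial mode and categorical time as fixed effects, plus covariates.

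The other scores defined there are a count of evidence-based interventions and six organizational-culture scores. None of them measures the availability of skills. The plan does not model availability or importance separately, and it does not say how to read a change in the gap when both ratings may have moved.

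The opening section gives the aim as testing whether active dissemination approaches improve perceived individual and organizational capacity for EBDM. The Power Analysis rests on three other outcomes: awareness, adoption and maintenance.

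**The concern.** A difference between two ratings reports only their net movement. Here the two ratings mean different things: availability is the capacity side of the trial's question, and importance reflects perceived need. If importance moves under the intervention, the gap can understate a gain in available skills, hide it, or show it with the opposite sign. It can also narrow when nobody has gained a skill.

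The intervention makes movement on both sides plausible. The activities table lists "In-state, in-person multi-day training in EBDM skills, 9 modules, as initial study intervention", which is directed at availability. The Organizational changes item of the intervention section includes work to "identify ways agency leadership can prioritize use of EBPPs, develop incentives for use of EBPPs". The same table also has leaders communicating their expectations for EBDM and treating it as a priority. Activities of that kind could raise how important staff rate the skills.

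At stake is the skill conclusion. A flat or wider gap could be reported as no effect or harm although available skills rose, and a narrower gap could be reported as a capacity gain although they did not.

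**Working it through.** **Inputs.** The gap definition, the averaging over 10 items and the model come from the Analysis Plan. The point changes used below are illustrative. The documents give no baseline means, SDs or expected changes for either rating.

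**The plan's own figure.** The stated range is -10 to +10. For a common rating scale, the range of a difference runs from (minimum - maximum) to (maximum - minimum). A 0-10 scale gives 0 - 10 = -10 to 10 - 0 = +10, and a 1-11 scale gives the same. A 1-10 scale would give -9 to +9. The anchors are not stated, so the range is reproduced on condition that the scale has 11 points. Nothing below depends on it.

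**The identity.** Write I and A for a respondent's mean importance and mean availability over the 10 skills. Then

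average gap = mean of (importance - availability) = I - A,

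and, because trial mode enters a linear model,

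effect on gap = effect on I - effect on A.

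Adjusting for time, degree, years worked, job category and accreditation does not separate the two terms. The identity holds for the effects being estimated. Three separately fitted mixed models need not subtract exactly, since each estimates its own variance components.

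**Same availability gain, different gap results** (negative means narrower):

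| Change in availability | Change in importance | Change in gap |
|---|---|---|
| +1.0 | 0 | 0 - 1.0 = -1.0 |
| +1.0 | +0.5 | 0.5 - 1.0 = -0.5 |
| +1.0 | +1.0 | 1.0 - 1.0 = 0 |
| +1.0 | +1.5 | 1.5 - 1.0 = +0.5 |

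**Same gap result, different availability:**

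| Change in availability | Change in importance | Change in gap |
|---|---|---|
| +1.0 | +0.5 | -0.5 |
| +0.5 | 0 | -0.5 |
| 0 | -0.5 | -0.5 |

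The first table shows a 1.0-point gain in availability appearing as a full effect, half an effect, none, or a wider gap. The second shows that a narrowing of 0.5 is compatible with availability gains of 1.0, 0.5 or zero. The gap estimate alone cannot choose between them.

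**The case against.** The strongest reply is that this is a choice of estimand. Importance minus availability measures unmet need. If both ratings rise equally, unmet need has not narrowed, and no change is the correct answer for that construct. This stands, and it is why the gap should be kept. It does not answer the capacity question, for which the gap has no companion estimate.

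A second reply is that capacity does not rest on this score: several culture scores bear on organizational capacity, and the gap is neither labelled primary nor used in the power analysis. This also stands. It limits the consequence, but none of those scores measures skill availability.

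Stronger readings that a reader might infer are not supported:

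- **That the intervention targets both ratings.** No text names higher importance ratings as an aim. The workshop objective to "understand the role of EBPPs in addressing the diabetes burden" concerns programs and policies, not how respondents rate 10 skills. The leadership activities make a rise plausible and no more. If importance is already rated near the top of the scale, it has little room to rise; the documents do not say.
- **That the gap is less precise than availability alone.** With equal SDs and correlation r between the ratings, the gap's SD is sqrt(2(1 - r)) times that of availability: 1.41 times at r = 0, 1.00 at r = 0.5 and 0.77 at r = 0.7. The direction depends on r, which is not given.
- **That averaging signed gaps is itself a fault to be corrected here.** The plan also calculates a gap for each skill, and means of the two ratings over the same 10 items would not remove offsetting between items.

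**Conclusion.** The point holds as a matter of algebra. The planned skill outcome gives the net of two effects, and by itself it cannot show whether available skills changed. For an availability gain of 1.0 point, the gap change runs from -1.0 to +0.5 as the rise in importance runs from 0 to 1.5. These values are illustrative, and the documents do not allow the likely size to be estimated.

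The conclusion rests on the gap being the only modelled skill score, which the Analysis Plan supports, and on importance being able to move, which is plausible but not shown. It would be too strong to infer that the gap is an invalid outcome, that importance will rise, or that the trial's overall conclusion depends on this score. This is a cheap improvement of limited consequence, not an error that undermines the trial.

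**What to change.** Keep the gap as planned. Fit the same mixed model to mean availability and to mean importance over the 10 items, as named supportive outcomes, and report the three estimates with confidence intervals side by side.

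Add a reading rule: a change in the gap, or the absence of one, is described as evidence about skill capacity only in light of the availability estimate and its interval. A narrower gap with no rise in availability is not read as a capacity gain. A flat or wider gap with a rise in availability is not read as no effect or as harm.

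The Analysis Plan mixes past and future tense and reports a factor analysis on all four time points, so survey data may already be in hand. If so, label the two models as added later.

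The cost is two further models on ratings already collected, a few sentences of text, and two more estimates to report, with no confirmatory claim attached to them.
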